| Objectives | 
First of all, this study is attempting to provide further clinical data on this medical devices for the post market clinical follow up. It will implement the knowledge of this device concerning its performance and its safety. It would consolidate the clinical follow-up dedicated to these devices.
 
Primary objective: The primary objective is to assess the significant clinical impact on patients treated for a total hip arthroplasty at their last follow-up (between 5 to 8 years) after surgery as a performance criteria.
 
Primary endpoint: The functional improvement following a total hip arthroplasty will be evaluated postoperatively at the last follow -up between 5 and 8 years postoperative years through the validated Oxford Hip Score.
 
Secondary objective: Preoperative clinical medical and surgical history will be harvested (Principal medical and surgical history, concomitant treatments if significative for the assessment of the pathology/treatment) to estimate the impact of comorbidity and risks factors on the pathology, and its reparation over time. Postoperative Radiological assessment of the reparation through pictures of the cotyles (face view) and femurs (face and profile views). The goals are to see the evolution of the reparation and moreover the interface behavior between prothesis and surrounding tissues; and if there's no displacement of the stems or more globally to the assembly along time.
 
• The face radiography of the femur and therefore of the stem will be appreciated to estimate a potential subsidence between the immediate postoperative period and middle term / long terms postoperative periods. The radiolucent line will be appreciated to emphasize of radiological level of loosening.• As well as the face femur picture, the profile view of the femur would inform (in another dimension) about a potential subsidence / or a radiolucent line confirming a radiological and/or a clinical loosening of stem, that can lead to a surgical revision.• The face radiography of the cotyle will mainly measured the inclination of the implant and its stability over time through its migration. The radiolucent line will be appreciated (De LEE and Charnley scales) to emphasize of potential radiological level of loosening. 
The daily physical activity will be harvested postoperatively to see the incidence of the reparation of the patient daily autonomy at their last timepoints.
 
The co-morbidity will be measured preoperatively and postoperatively using the Charnley classification. The goal is to estimate if the co-morbidity may be detrimental to the clinical results and their evolution and potentially to identify the nature of detrimental factors.
 
All complications will be recorded during the study. A global survival rate would therefore be calculated at each timepoints. As the same manner, an aseptic loosening rate and a global
 |

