Number of needed patients:

The number of needed patients was determined arbitrarily and is based on an estimated sufficient number to have a real incidence when means will be calculated.

→Number of patients in the cohort: 120

| | |
|-----------------------|---|
| Collected data | 
Preoperative phase:
 
Sociodemographic data: age, sex, weight, height
 
Medical & surgical history, risk factors and comorbidities
 
Primary diagnosis and operative indication.
 
Daily physical activities
 
Charnley Classification
 
Operative & immediate postoperative phases :
 
Perioperative & immediate postoperative complications;
 
Surgery description (assembly of components and sizes, description of the devices used in combination with Sagitta EVL-R stems);
 
Immediate postoperative radiologic evaluation;
 
Post-operative data (6 months, 1, 2, 5, and potentially between 5 to 8 years):
 
Radiologic evaluation (inclination of the cup, localization of the rotation center, presence of periprosthetic radiolucent line for the cup and the stem, height of the stem comparing with an anatomic locator)
 
Postoperative data through unique individual phone call corresponding to 5 to 8 postoperative years:
 
 - Oxford clinical scores - Daily physical activities - Global outcomes: Patient's satisfaction, walking ability, functional improvement, |
|-----------------------|---|

| | | | |
|---|--------------------------------|---|-------------------------------|
|  | Document No. 2019-10-EVLR-N | SAGITTA EVL-R STEMS – NOVAE / SAGITTA EVL-R CUPS | ID RCB : 2019-A01777-50 |
| | Version 02 | | Page No. Page 8 sur 28 |

release pain
- Charnley Classification

Postoperative complications all over the follow-up of patients between the preoperative period until the phone call (5 to 8 years)

| | | | |
|--|----------------------------------|---|---|
|  serf | Document No. | SAGITTA EVL-R STEMS – NOVAE / SAGITTA EVL-R CUPS | ID RCB : 2019-A01777-50 |
| | 2019-10-EVLR-N Version 02 | | |
| | | | Page No. Page 9 sur 28 |

ABBREVIATIONS

| | |
|-------------|---|
| AAOS | American Academy of Orthopaedic Surgeons |
| ADE | Adverse device Effect |
| AE | Adverse Event |
| BMI | Body Mass Index |
| CRF | Case Report Form |
| HAS | Haute Autorité de Santé |
| HHS | Harris Hip Score |
| NICE | National Clinical Guideline Centre |
| OHS | Oxford Hip Score |
| SAE | Serious Adverse Event |

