6.1 Primary objective

The primary objective is to assess the significant clinical impact on patients treated for a total hip arthroplasty at **their last** follow-up (between 5 to 8 years) after surgery as a performance criterion.

6.2 Secondary objectives:

Preoperative clinical medical and surgical history will be harvested (Principal medical and surgical history, concomitant treatments if significative for the assessment of the pathology/treatment) to estimate the impact of comorbidity and risks factors on the pathology, and its reparation over time.

| | | | |
|--|------------------------------|---|--------------------------------|
|  serf | Document No. | SAGITTA EVL-R STEMS – NOVAE / SAGITTA EVL-R CUPS | ID RCB : 2019-A01777-50 |
| | 2019-10-EVLR-N Version 02 | | |
| | | | Page No. Page 16 sur 28 |

Postoperative Functional improvement periods following a total hip arthroplasty.

Postoperative Radiological assessment of the reparation through pictures of the cotyles (face view) and femurs (face and profile views). The goals are to see the evolution of the reparation and moreover the interface behavior between prothesis and surrounding tissues; and if there's no displacement of the stems or more globally to the assembly along time.

- The face radiography of the femur and therefore of the stem will be appreciated to estimate a potential subsidence between the immediate postoperative period and middle term / long terms postoperative periods. This subsidence can potentially be a primary step to a loosening. The radiolucent line will be appreciated to emphasize of radiological level of loosening. This finding may have no clinical impact on the patient daily life. It will depend of the level of loosening of the cup and its evolution. Generally, a clinical impact is regularly associated with failure and/or pain; thus necessitating a surgical revision. Tangsatapron et al. have analyzed that risks factors inducing femoral stem subsidence were the weight of patients and long sizes of stems and more particularly a medial-lateral stem-bicortical fit less than 2cm (Tangsataporn et al. 2015). Ries et al. have shown that the subsidence was statistically higher in patients collarless stems than with collar (Ries et al. 2019). Girard et al. have emphasized that the bad quality of the osseointegration of the stem is risk factor for subsidence (Girard et al. 2011).

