6.3 Primary endpoint

The clinical improvement at the postoperative periods will be evaluated postoperatively at the last follow-up using through the validated Oxford Hip Score and with its primary interpretation. The Oxford Hip Score (OHS) is a short 12-item patient-reported PRO specifically designed and developed to assess function and pain with patients undergoing hip replacement surgery. It is short, reproducible, valid and sensitive to clinically important changes. The overall time needed to fill for the patient is about 5 to 7 minutes. There are a dozen of items. The score has a maximum of 60 points (worst possible outcome) and a minimum of 12 points (best possible score). The OHS is a patient self-completion PRO containing 12 questions on activities of daily living. The OHS has been developed and validated specifically to assess function and pain for patients undergoing total hip replacement (THR) surgery. The OHS is the most evaluated hip specific measure available.

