6.4 Secondary endpoints

The endpoints are:

- The functional improvement following a total hip arthroplasty will be evaluated postoperatively at the

| | | |
|---|---|---------------------------------------|
|  Document No. 2019-10-EVLR-N | SAGITTA EVL-R STEMS – NOVAE / SAGITTA EVL-R CUPS | ID RCB : 2019-A01777-50 |
| | Version 02 | Page No. Page 17 sur 28 |

last follow -up between 5 and 8 years postoperative years through the validated Oxford Hip Score

- The daily physical activity will be appreciated postoperatively at the last follow-up postoperatively.
- The co-morbidity will be measured preoperatively and postoperatively at 6 months, 1, 2, 5, and potentially between 5 to 8 years postoperatively.
- The global satisfaction of patients will be measured at the last follow -up between 5 and 8 years postoperative years.
- The walking ability will be measured at the last follow-up between 5 and 8 years postoperative years.
- The global functional improvement will be measured at the last follow-up between 5 and 8 years postoperatively.
- The pain release will be estimated at the last follow-up between 5 and 8 years postoperatively.
- The length of the operated limb will be harvested at 6 months, 1, 2, 5 and/or at 5 to 8 years postoperatively, if available.
- Adverse events all along the postoperative follow-up and if the information is available in patients' files:
 - Nature and origins of complications.
 - graded as serious (leading to death, life-threatening condition, requiring hospitalization or lengthening of hospital stay, leading to permanent or significant disability);
 - or graded as not serious and as implant-related (migration, subsidence) or surgery-related (iatrogenic event) or other relationships (i.e. aseptic loosening...), idiopathic events, possible related pathology events, but not limited to.

6.5 Secondary radiographic outcomes:

Postoperative Radiological assessments will be followed at immediate postoperative period and at 6 months, 1, 2, 5, and potentially between 5 to 8 years postoperatively. The inclination of the cup, the localization of the center of rotation, and the presence or not of a periprosthetic radiolucent line will be followed and its location. Moreover, the distance, the height of the stem comparing with an anatomic locator (greater or lesser trochanter) and the presence or not of a periprosthetic radiolucent line all around and its location.

7 Study design

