8.5 Exclusion criteria

After inclusion, patients can be excluded from the study if the final follow up is 24 months and if available data at the 24 months postoperative visit is too poor.

9 Study procedures

Patient information:

This observational study does not require any additional eligibility criteria, any additional exam. According to French regulation, each patient is appropriately informed of his/her freedom to decline or agree to participate to the study (thanks to the information note) and of his rights regarding medical data collection.

Study withdrawal:

Patients may withdraw from the study at any time at their own request, or they may be withdrawn at any time at the discretion of the investigator or sponsor for safety, behavioral, or administrative reasons. In any circumstance, every effort should be made to document patient outcome, if possible.

| | | | | | |
|--|----------------|---|-------------------------|----------------|--|
|  serf | Document No. | SAGITTA EVL-R STEMS – NOVAE / SAGITTA EVL-R CUPS | ID RCB : 2019-A01777-50 | | |
| | 2019-10-EVLR-N | | Page No. | Page 19 sur 28 | |

10 Collected data

Patients will be followed at 2 stages: in their medical history files and through a phone call [after](#) the surgery.

| Endpoints | Preoperative | Per-operative | Immediate post-operative | Visit 6 months | Visit 1 year | Visit 2 years | Last visit over 2 years | Phone call to patients |
|--|---|---------------|--------------------------|----------------|--------------|---------------|-------------------------|------------------------|
| Patient information (gender, age, weight, height) | X | | | | | | | |
| Eligibility criteria | X | | | | | | | |
| Medical & surgical history | X | | | | | | | |
| Oxford questionnaires | | | | | | | | X |
| Daily physical activity | | | | | | | | X |
| Charnley Classification | X | | | X | X | X | X | X |
| Surgery - Assembly components description | | X | | | | | | |
| Peroperative Incidents | | X | | | | | | |
| Global results: Patient satisfaction Walking ability Functional improvement Pain release | | | | | | | | X |
| Length of the operated limb | | | | | | | | X |
| Radiologic assessment | Inclinaison of the Cup and localization of the center of rotation | | X | X | X | X | X | X |
| | Periprosthetic radiolucent line - Cup | | X | X | X | X | X | X |
| | Stem height/ anatomic locator | | X | X | X | X | X | X |
| | Periprosthetic radiolucent line - stem | | X | X | X | X | X | X |

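### The primary endpoint is called improvement on the Oxford Hip Score, but the score is taken only once, 5 to 8 years after surgery, so it can show status and not change

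*Protocol*

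**What the plan says.** **Objective.** The summary states: "The primary objective is to assess the significant clinical impact on patients treated for a total hip arthroplasty at their last follow-up". Section 6.1 says the same, and both place that follow-up between 5 and 8 years and call it a performance criterion.

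**Primary endpoint.** The summary has: "The functional improvement following a total hip arthroplasty will be evaluated postoperatively at the last follow -up between 5 and 8 years", measured with the Oxford Hip Score. Section 6.3 has: "The clinical improvement at the postoperative periods will be evaluated postoperatively at the last follow-up using through the validated Oxford Hip Score". It adds that the score will be used with its primary interpretation, and gives a range from 12 (best) to 60 (worst).

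**Same label elsewhere.** Section 6.4 lists OHS functional improvement again as a secondary endpoint, at the "last follow -up between 5 and 8 years postoperative years through the validated Oxford Hip Score". Section 10.5 puts the heading of functional improvement over the OHS taken by phone. Section 6.2 has a secondary objective worded "Postoperative Functional improvement periods following a total hip arthroplasty", which does not name a scale.

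**Data collection.** The summary lists the OHS only under "Postoperative data through unique individual phone call corresponding to 5 to 8 postoperative years". In Table 1 (section 10) the row reads "Oxford questionnaires | | | | | | | | X", where the last column is the phone call. Section 10.5 says the questionnaire is completed by phone with the patient.

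**The concern.** Improvement means a difference between two states of the same patient. The protocol plans to observe only the later one. A good score 5 to 8 years after surgery may follow a large gain, a small gain or none, and the score alone cannot tell these apart.

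This is the primary performance result. Section 6 says the results will serve as a basis for the indications currently claimed for the device, and section 16.1 gives proof of performance and safety in those indications as their main use. Followed as written, the report would present one late score as improvement. Survival, loosening, complication and radiographic results need no OHS baseline and are not touched.

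**Working it through.** The protocol gives no figure to reproduce here: the sample of 120 is declared arbitrary and is not derived from any OHS change. The check sets the endpoint against the schedule.

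**1. Count the OHS assessments.** Table 1 has 8 columns: preoperative, per-operative, immediate postoperative, 6 months, 1 year, 2 years, last visit over 2 years, and phone call.

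- OHS: marked in 1 of 8 columns (phone call).
- Charnley classification: "Charnley Classification | X | | | X | X | X | X | X", marked in 6 of 8 columns, the preoperative one included.
- Rows marked preoperatively: 4 (patient information, eligibility, medical and surgical history, Charnley). None is the OHS.

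Charnley is a co-morbidity class and not an outcome score. It shows only that the table records before-and-after measurement where this is planned.

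**2. Look for a baseline elsewhere.** The preoperative list (section 10.1) and the list for 6 months to 8 years (section 10.4) contain no OHS. No retrieval of an earlier score from files and no recalled preoperative score is described. Patients were operated on between 2011 and 2014 and the study was to start in November 2019 (summary; section 7.3), so a preoperative OHS can no longer be taken.

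**3. Compute what can be computed.** With B the preoperative score and F the score at the call, and lower being better:

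improvement = B − F

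F is observed and B is not. Patients with both: 0 of 120. The 12-to-60 scale bounds improvement only between 12 − F and 60 − F, a width of 60 − 12 = 48 points, which is the whole scale. Even the best possible score, F = 12, fits any improvement from 12 − 12 = 0 to 60 − 12 = 48 points.

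**4. Ask whether other planned data fill the gap.**

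- *Comparison with the literature (section 13.2).* It can set the observed level beside published levels. It cannot give these patients' starting point.
- *Closed questions on satisfaction, walking, function and pain (sections 6.4 and 10.4).* These are separate secondary items and do not turn the OHS into a change score. Table 1 marks them at the phone call only, so any answer about change would presumably rest on recall. The protocol does not say so, and the case report form is not shown.

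**5. Count the places affected.** The OHS improvement label stands in the summary and in sections 6.3, 6.4 and 10.5: 4 places. The secondary objective in section 6.2 uses similar wording without naming the OHS.

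**The case against.** The strongest reply is that this is a label and not a design fault. The protocol defines no change score, baseline or paired test. Every statement of the primary endpoint is fixed at the last follow-up, and section 10.5 explains its own heading as an assessment of the results of surgery at that time. On that reading the intended quantity is a postoperative level, which can be collected and reported. Section 6.3 also refers to a primary interpretation of the score, and the contents list an appendix on its calculation (19.1) that was not available for this review.

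Much of this is fair, and it may well describe what the sponsor intends. It does not rescue the text. If status is meant, the word improvement is wrong and the remedy is to replace it. If improvement is meant, it cannot be estimated. Neither the interpretation clause, nor an appendix on scoring, nor a statistical analysis plan can supply a baseline that is never collected.

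Three lesser points stand. Section 6.2 does not name the OHS, so its objective may refer to the closed question on function. Section 13.2 speaks of frequencies and percentages and says nothing of precision, so a request for precision adds to the plan. The lack of a control group has no bearing on within-patient change: the missing baseline alone carries the argument.

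**Conclusion.** The concern holds. The primary endpoint as named cannot be estimated for any of the 120 planned patients, because the plan yields one OHS per patient and no preoperative one. What the plan can deliver is the OHS level, covering pain and function, at 5 to 8 years.

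The conclusion rests on the endpoint wording and the schedule in the protocol, with no outside figure. It makes no claim about how much patients improved, in which direction, or whether the OHS suits this population. Whether some hospital files hold a preoperative OHS is unknown; the protocol plans no use of one. Because this is the primary endpoint of a study meant to support the claimed indications, it should be corrected.

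**What to change.** 1. Restate the primary objective and endpoint (summary, 6.1, 6.3) and the heading in 10.5 as OHS status at last follow-up, 5 to 8 years after surgery. Describe it with a measure of precision and set it against published values, as section 13.2 already foresees for all data. State that no conclusion of improvement will be drawn from the OHS.
2. Delete the OHS functional improvement entry among the secondary endpoints in 6.4, which repeats the primary one. Reword the related secondary objective in 6.2 so that it names its measure.
3. Report the closed questions on function, walking and pain apart from the OHS, and as patient-recalled change if that is how they are asked.

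**Cost.** Wording in the summary and sections 6.1 to 6.4 and 10.5, plus a line in 13.2 for precision unless the analysis plan covers it. No new patients, visits or data items. The primary claim becomes more modest: status at 5 to 8 years in place of improvement.

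If the sponsor wishes to keep improvement, the protocol would have to name a source of preoperative OHS values in the files, add it to section 10.1 and Table 1, and say how patients without one are handled. Nothing in the protocol shows that such values exist.

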6.4 Secondary endpoints

The endpoints are:

- The functional improvement following a total hip arthroplasty will be evaluated postoperatively at the

| | | |
|---|---|---------------------------------------|
|  Document No. 2019-10-EVLR-N | SAGITTA EVL-R STEMS – NOVAE / SAGITTA EVL-R CUPS | ID RCB : 2019-A01777-50 |
| | Version 02 | Page No. Page 17 sur 28 |

last follow -up between 5 and 8 years postoperative years through the validated Oxford Hip Score

- The daily physical activity will be appreciated postoperatively at the last follow-up postoperatively.
- The co-morbidity will be measured preoperatively and postoperatively at 6 months, 1, 2, 5, and potentially between 5 to 8 years postoperatively.
- The global satisfaction of patients will be measured at the last follow -up between 5 and 8 years postoperative years.
- The walking ability will be measured at the last follow-up between 5 and 8 years postoperative years.
- The global functional improvement will be measured at the last follow-up between 5 and 8 years postoperatively.
- The pain release will be estimated at the last follow-up between 5 and 8 years postoperatively.
- The length of the operated limb will be harvested at 6 months, 1, 2, 5 and/or at 5 to 8 years postoperatively, if available.
- Adverse events all along the postoperative follow-up and if the information is available in patients' files:
 - Nature and origins of complications.
 - graded as serious (leading to death, life-threatening condition, requiring hospitalization or lengthening of hospital stay, leading to permanent or significant disability);
 - or graded as not serious and as implant-related (migration, subsidence) or surgery-related (iatrogenic event) or other relationships (i.e. aseptic loosening...), idiopathic events, possible related pathology events, but not limited to.

6.5 Secondary radiographic outcomes:

Postoperative Radiological assessments will be followed at immediate postoperative period and at 6 months, 1, 2, 5, and potentially between 5 to 8 years postoperatively. The inclination of the cup, the localization of the center of rotation, and the presence or not of a periprosthetic radiolucent line will be followed and its location. Moreover, the distance, the height of the stem comparing with an anatomic locator (greater or lesser trochanter) and the presence or not of a periprosthetic radiolucent line all around and its location.

7 Study design

